7.0 Data and Specimen Banking*

During the data cleaning period at the end and following conclusion of the study, the data will be thoroughly searched for any identifiers, so that data storage on a long-term basis, will be stripped of identifiers.

PROTOCOL TITLE: The Center for Enhancing Treatment & Utilization for Depression and Emergent Suicidality Phase 1b-Study 3-BRITEPath

Identifiable data collected by the study will be contained in secure, firewall-protected servers managed by Pitt/CSSD-NOC and will only be accessible by the research team.

We assure that the private information gathered as part of this study will not be reused or disclosed to any other person or entity, except when required by law, for authorized oversight of the study, or for other research for which the IRB has granted a waiver of written HIPAA authorization.

At the request of another researcher, we will provide de-identified data sets only via encrypted documents. The research statistical coordinator and data manager will keep a log of data shared.

Sharing Data with Kaiser Permanente:

Data from the CASA, Child and Adolescent Services Assessment and E-HR will be collected in order to meet the study aims of conducting cost analyses on ETUDES center research pilot studies, including BRITEPath. We are sending a limited set.

Data we are sharing includes responses from the Child and Adolescent Services Assessment (CASA) that is administered to both parent and child participants at baseline and all follow up visits. A limited data set of the CASA will be shared including all service utilization fields except names of facilities/providers. We also recode any date into “days since baseline.” The investigators will collect electronic health record data including:

- 1) Service Utilization: # Visits (PCP, MH specialty, ER, hospitalizations); pharmacotherapy; medical/psychiatric comorbidity; Insurance coverage;
- 2) Personalized referral: Match to Screening Wizard & expert opinion;
- 3) Application utilization: Use of technical components of interventions & web portals (Text2Conect, BritePath);
- 4) Provider uptake: # Providers engaging in training/intervention % Representation at practice site; and
- 5) Practice uptake: # Practices who deliver intervention.

8.0 Sharing of Results with Subjects*

Upon publication of primary outcome paper, participants will be informed through a preferred contact method of the publication. No subjects will be identified without explicit and written consent in any publications that come from this project.

9.0 Study Timelines*

The duration of an individual subject’s participation in the study is 12 weeks.

The duration anticipated to enroll all study subjects will be from 8/2019-2/2020.

PROTOCOL TITLE: The Center for Enhancing Treatment & Utilization for Depression and Emergent Suicidality Phase 1b-Study 3-BRITEPath

The estimated date for the investigators to complete this study (complete primary analyses) is 4/2022.

10.0 Inclusion and Exclusion Criteria*

Individuals will be screened for eligibility via phone or after presenting to the site's clinical setting with an eligibility script and inclusion/exclusion questions. Responses to the questions will be entered into a secure study database managed by the University of Pittsburgh housed on a secure, encrypted server behind University firewall. Individual logins will be provided to research/site staff associated with this project.

Inclusion Criteria:

- Youth aged 12-26 yo
- Own a device (e.g. smartphone, ipod, tablet) with capability to download BRITE app
- Biological or adoptive parent is willing to provide informed consent for teen to participate
- Youth speaks and understands English
- Positive PHQ score or provider determines patient has depressive symptoms based on clinical interaction and refers youth to the study (in cases when PHQ is not available OR provider/parent have concern that youth/patient has a mood or behavioral problem
- Family agrees to see a MH staff at the site

Exclusion Criteria:

- Non English speaking
- No parent willing to provide informed consent for minors
- No cell phone capability of downloading BRITE app
- Is currently experiencing mania or psychosis symptoms that would prevent participant from understanding/participating
- Evidence of an intellectual or developmental disorder (IDD)
- Life threatening medical condition that requires immediate treatment (included emergent suicidality, homicidality, abuse/neglect, or other mental or physical condition)
- Other cognitive or medical condition preventing youth from understanding study and/or participating.
- Adults unable to consent
- Pregnant women-not specifically included or excluded as intervention and research procedures conducted will not inquire if a woman is pregnant.

-Prisoners excluded

11.0 Vulnerable Populations*

Children ages 12-17 will be recruited through their parents and not directly advertised to with study information. Legal guardians with proper court paperwork, biological and/or adoptive parents will provide permission for their child to participate. The child will receive study information via email/mail and over the phone to aid in their understanding of the study procedures and trained clinical assessors will explain the procedures using language appropriate for their age/grade level. See consent process for additional details.

12.0 Local Number of Subjects

We expect to recruit about 10 subjects locally at each site onboarded to BRITEPath study as eligible and completed informed consent, and intervention with site clinicians.

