PROTOCOL TITLE: The Center for Enhancing Treatment & Utilization for Depression and Emergent Suicidality Phase 1b-Study 3-BRITEPath

parents and patients. The simplicity and flexibility of BRITEPath would allow for its dissemination to reach beyond specialty MH clinics and is consistent with the NIMH 2015 Strategic Plan emphasizing the need for individualized strategies to improve patient outcomes.

It is impractical for MH clinicians to offer BRITEPath only sometimes and to some patients and not others. Although a cluster randomized trial could address this issue, this design is not feasible for a pilot study. Thus, we will utilize a stepped wedge design in which all practices start with Treatment As Usual (TAU) initially and are randomly chosen to transition to BRITEPath at different times. All clinics will be initially monitored for at least two months during TAU for the main outcomes of fidelity to delivery of the intervention. This will be followed by a staggered adoption of BRITEPath. At each time period, a new clinic will begin implementing the intervention. Block randomization determines the order each clinic begins BRITEPath. Each time period (approximately 3 months), a web-based system will be used to assign the next clinic to begin using BRITEPath.

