17.0 Data Management* and Confidentiality

A stepped wedge design was selected for both ethical considerations and feasibility. A stepped- wedge cluster randomized trial design involves the sequential random rollout of an intervention over multiple time periods following a “baseline” period when no cluster has been exposed. The crossover is typically in one direction, from control to intervention, and continues until all of the clusters receive the intervention with observations taken from every cluster and at each time period. All 3 studies in the ETUDES Center, and specifically, BRITEPath, will utilize this design. Prior to study start, each site will be randomly assigned to switch from.

Treatment As Usual (TAU) to the intervention. In the proposed stepped wedge design, all practices start with TAU (i.e., PCP referral to embedded MH care) and are randomized to transition to implement BRITEPath at different times. All clinics will be initially monitored for at least 2 months during TAU, followed by a staggered adoption of BRITEPath. During each time period, a new clinic will begin to use BRITEPath (order determined by block randomization). A webbased system will randomly assign the next clinic to begin.

With regard to the stated hypothesis: We will perform multilevel modeling to explore time- and intervention-level factors associated with BRITEPath’s use. We will first conduct t-tests for continuous variables and chi-square tests for categorical variables to examine baseline differences in demographic and clinical variables. We will use generalized linear mixed models (nesting for site) to examine between intervention differences in readiness. Distinguishing characteristics will be included as covariates in models examining treatment effects.

Due to the pilot nature of this study, sample size and power considerations center around the precision of confidence interval (CI) width estimation for feasibility outcomes. In this development phase (Aim 1), a sample size of 50 affords us a 95% CI width of no more than 0.28.

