26.0 Multi-Site Research*

26.1 Study-Wide Number of Subjects: 50

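### About 10 per site and 50 overall are not allocated by rollout step or condition; if TAU patients count, the planned enrolment window implies only 8-10 BRITEPath patients

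*Combined protocol and SAP*

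**What the plan says.** **Numbers.** Section 12.0 states: "We expect to recruit about 10 subjects locally at each site onboarded to BRITEPath study". The same sentence goes on to describe these subjects as eligible and as having "completed informed consent, and intervention with site clinicians". The study-wide figure is "26.1 Study-Wide Number of Subjects: 50". No section gives the number of clinics, a recruitment rate, or a number by step or condition.

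**Rollout.** Section 6.0 says "All clinics will be initially monitored for at least two months during TAU". After that, "At each time period, a new clinic will begin implementing the intervention", and the step length is given by "Each time period (approximately 3 months), a web-based system will be used to assign the next clinic". Section 17.0 describes the crossover in such a design as one that "continues until all of the clusters receive the intervention with observations taken from every cluster and at each time period".

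**Timing.** Section 9.0 states: "The duration anticipated to enroll all study subjects will be from 8/2019-2/2020".

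**Use of the numbers.** Section 17.0 bases the sample size on a 95% confidence interval no wider than 0.28 with 50 participants. The criterion for success in section 2.2 is 75% use among adolescents who receive BRITEPath. Hypothesis 1b, in the same section, compares BRITEPath with TAU.

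**The concern.** In a stepped wedge, the number enrolled in each clinic and step determines how many patients receive the intervention and which clinics contribute to both conditions. A flat target leaves that to recruitment speed. Clinics that cross late spend most of the rollout in TAU. If TAU patients count towards the target, those clinics can use up their places before they cross.

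Two things are at stake. The 75% use criterion has BRITEPath recipients as its denominator, so a small number of recipients makes the interval much wider than the plan says. The criterion for clinicians' use of the tools would also be judged in only the clinics that enrolled under BRITEPath. If the 10 are all intervention patients, the difficulty moves to the other arm: nothing is planned for TAU, although Hypothesis 1b needs it.

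**Working it through.** **1. The plan's own figure.** Wald width = 2 x 1.96 x sqrt(p(1-p)/n). With p = 0.5 and n = 50: 2 x 1.96 x sqrt(0.25/50) = 0.277, which agrees with the stated maximum of 0.28. The figure therefore needs all 50 in the denominator.

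**2. Inputs.**
- From the documents: about 10 per site (12.0), 50 overall (26.1), at least two months of TAU, one clinic crossing about every three months (6.0), enrolment 8/2019-2/2020, or 6-7 months (9.0).
- Assumed: 50/10 = 5 clinics, all opening together, equal steady recruitment, TAU patients counted, a clinic stops at 10.

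**3. Crossing times.** Clinic k crosses at month 2 + 3(k-1): months 2, 5, 8, 11 and 14. The last three-month step ends at month 17.

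**4. Rate implied by the window.** 10/7 = 1.43 to 10/6 = 1.67 per clinic per month.

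**5. Enrolment by condition.** At rate r, clinic k enrols min(10, r x crossing month) under TAU and the rest of its 10 under BRITEPath.
- r = 1.43: clinic 1 has 10 - 2.86 = 7.14 under BRITEPath and clinic 2 has 10 - 7.14 = 2.86. Clinics 3-5 are full at month 7 and have none. Total 10 BRITEPath, 40 TAU.
- r = 1.67: clinic 1 has 6.67 and clinic 2 has 1.67. Clinics 3-5 are full at month 6 and have none. Total 8.3 BRITEPath, 41.7 TAU.

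With random (Poisson) arrivals at these rates, the simulated probability that most clinics have no BRITEPath patient is 0.73-0.89.

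**6. Sensitivity to the rate.** The last column is the standard error of the BRITEPath-TAU contrast, in SD units. It comes from generalised least squares with step fixed effects, a clinic random intercept, an assumed ICC of 0.05 and one outcome per person.

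| Rate per clinic-month | BRITEPath, clinics 1-5 | Total BRITEPath | Total TAU | Clinics with none | SE |
|---|---|---|---|---|---|
| 0.6 | 8.8, 7.0, 5.2, 3.4, 1.6 | 26 | 24 | 0 | 0.40 |
| 1.0 | 8, 5, 2, 0, 0 | 15 | 35 | 2 | 0.38 |
| 1.43-1.67 | 6.7-7.1, 1.7-2.9, 0, 0, 0 | 8-10 | 40-42 | 3 | 0.42-0.44 |
| 2.0 | 6, 0, 0, 0, 0 | 6 | 44 | 4 | 0.50 |

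Clinic 3 fills before it crosses when r is at least 10/8 = 1.25. With a three-month first period that threshold is 10/9 = 1.11, and the window rate gives 5-7 BRITEPath patients with 3-4 clinics empty.

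**7. Interval width for BRITEPath use.**
- n = 8: 0.69 at p = 0.5; 0.60 at p = 0.75.
- n = 10: 0.62 at p = 0.5; 0.54 at p = 0.75.
- n = 25: 0.39 at p = 0.5; 0.34 at p = 0.75.

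**8. The other reading.** If the 10 are all intervention patients, 5 x 10 = 50 uses the whole sample and leaves 50 - 50 = 0 planned for TAU.

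**9. The window against the rollout.** A window of 6-7 months includes the crossings at months 2 and 5 and closes before month 8. Clinics 3-5 then enrol nobody under BRITEPath even without a limit of 10.

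**The case against.** The strongest objection is textual. Read literally, section 12.0 counts patients who have completed the intervention. Section 22.0 has staff start BRITEPath once consent is given, and section 25.1 speaks of approaching patients to pilot the app. On that reading no clinic can fill up under TAU. This stands as a reading, but it leaves the TAU arm without a planned number, so it replaces one gap with another.

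Second, the figure of about 10 is an expectation, not a cap, and five clinics opening together is an inference. That is right. The overall 50 still bounds the total, however, so early TAU enrolment uses up places. With three or four clinics and a two-month first period, most clinics would be left without a BRITEPath patient only at 2 or more per month.

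Third, a reader might infer that most clinics would never enrol a BRITEPath patient at any ordinary recruitment speed, or that the flat target can never deliver both conditions in every clinic. The documents do not support either. They state no rate, and the one implied by section 9.0 may be out of date, because other sections refer to the COVID-19 pandemic. At 1 per month three of five clinics enrol under BRITEPath, and at 0.6 all five do.

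Fourth, a reader might infer that condition would be largely confounded with clinic. The standard errors do not bear that out: 0.38 at 1 per month is no worse than 0.40 at the slow pace, and the clear loss comes only at about 2 per month or more.

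Finally, the bi-weekly calls in section 26.3 already review enrolment targets. They can monitor an allocation, but the plan gives them none to monitor.

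**Conclusion.** The concern holds in conditional form. The plan has no allocation by step or condition and does not say whether TAU patients count towards the 10.

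- If they count, with five clinics opening together and recruitment at the rate implied by section 9.0, about 8-10 of 50 would receive BRITEPath, in two of five clinics. The interval for use would be 0.62-0.69 wide at p = 0.5 (0.54-0.60 at p = 0.75) instead of 0.28. The main loss is in the number of recipients and the coverage of clinics; the contrast with TAU is only modestly less precise.
- If they do not count, Hypothesis 1b has no planned comparator number.

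The size of the first result depends on the rate and shrinks below about 1.25 per clinic per month. What does not depend on the rate is that the enrolment window and a rollout whose fifth crossing falls at month 14 or later cannot both hold for five clinics.

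**What to change.** In section 12.0, state the number of clinics and whether the 10 includes TAU patients. Replace the flat figure with an enrolment target per clinic and step, the same in TAU and BRITEPath steps. For five clinics and six steps this is 50/30, or about 1.7. Of the 30 clinic-steps, 5 + 4 + 3 + 2 + 1 = 15 fall under BRITEPath, so equal numbers per step give 25 and 25. An even monthly rate over 17 months gives about 24 TAU and 26 BRITEPath. Either way all five clinics contribute to both conditions. Track the target on the existing bi-weekly calls.

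Reconcile the 8/2019-2/2020 window in section 9.0 with the rollout in sections 6.0 and 17.0. Without that, a target per step cannot work: about three steps at 1-2 per clinic would yield only 15-30 participants. In section 17.0, restate the interval width for the planned number of BRITEPath recipients, about 0.39 for 25 at p = 0.5.

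The cost is a short change of text. In practice, busy clinics may have to pause recruitment, and enrolment must run for the full rollout.

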We will develop an app-based intervention, BRITEPath that enhances the capacity of pediatric primary care to effectively manage depressed and suicidal adolescents by referral to embedded MH services. BRITEPath includes three components delivered by MH clinicians, including (1.) an electronic on-boarding procedure tool that supports MH clinicians, Guide2Brite; (2.) the adolescents' safety planning app, BRITE; and (3.) the clinician dashboard, BRITEBoard, to facilitate treatment planning and communication with other primary care providers.

2.2 The aims and hypotheses related to this specific protocol and submission are below for Phase 1b. Aims of the previous phase are in a University of Pittsburgh OSIRIS IRB protocol submission (#PRO18050281) entitled ETUDES Phase 1a-qualitative. Aims of later phases described briefly will be submitted in subsequent protocols.

PROTOCOL TITLE: The Center for Enhancing Treatment & Utilization for Depression and Emergent Suicidality Phase 1b-Study 3-BRITEPath

We will test the feasibility of using BRITEPath in community & pediatric practices using a stepped wedge design. We hypothesize that participants, parents, and clinicians will find the intervention usable and feasible to deploy. We will assess the impact of BRITEPath alone (compared to its impact as part of iCHART in later phases of the ETUDES Center, by obtaining follow-up phone assessments on suicidality, depression, and functional status at 4 and 12 weeks after intake.

Aim 1b (Phase 1b, Feasibility). We will pilot BRITEPath in sites using a stepped wedge design (50 adolescents aged 12-26 yo). Hypothesis 1b: The use of BRITEPath will decrease depressive symptoms, distress, and suicidality (any self-injurious ideation, urges, or behavior) as well as improve overall functioning compared to TAU.

Criterion for success: 75% of adolescents who receive BRITEPath will use it, and 75% of MH clinicians will use Guide2BRITE and BRITEBoard.

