13.0 Recruitment Methods

Participants will be screened through site staff and clinicians under the direction of the site investigators. Clinicians taking part in the research project will scan intakes via telehealth (or in person when the COVID-19 pandemic allows for in person procedures) appointments for eligibility by reviewing electronic medical record information and chief complaint for presenting to appointment. At time of appointment, trained clinician/research site staff will discuss BRITEPath study option and complete eligibility screening questions.

Flyers and informed consent fact sheets used to discuss procedures and risks/benefits may be emailed or mailed for the patient to view at any time.

Participants are provided with the BRITE app during this appointment following completion of the intervention. Upon responding to follow up phone calls made by Pittsburgh/ETUDES Center research staff, the participants will be paid up to \$180 on a visa gift card type card and mailed to participants' address.

Baseline visit phone call after intervention completed at site: \$40

Week 4 Follow Up call: \$60

Week 12 Follow Up call: \$80

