22.0 Consent Process

INFORMED CONSENT/ *Subjects who are not yet adults (infants, children, teenagers)*

Trained research/site staff will complete verbal informed consent with participant over the phone and provide a copy of the document via email or mail. Upon obtaining informed consent, the site staff will initiate the BRITEPath intervention. Following the intervention, Pittsburgh/ETUDES Center research staff will follow up and complete research phone calls for which participants will be paid.

PROTOCOL TITLE: The Center for Enhancing Treatment & Utilization for Depression and Emergent Suicidality Phase 1b-Study 3-BRITEPath

During the informed consent discussion, the site staff will speak with the parent to obtain permission to enroll the teen in this study and consent for her or his own participation. The staff will also speak with the adolescent to obtain her or his assent. The assessor will ask the family to take the phone call in a private location to decrease confidentiality breaches and discomfort about talking about sensitive topics.

During the consent process, research/site staff will make it clear that participation is voluntary to both the parent and child participants or adult participant if they are 18 at the time of enrollment. If a minor turns 18 years old during the course of the study an additional consent process will occur via the phone to ensure ongoing willingness to participate that Pittsburgh/ETUDES trained research staff will conduct. During each baseline and follow up phone call, Pittsburgh/ETUDES trained research staff will ascertain if the parent and child are still interested in participating in the study questions prior to collecting or updating data. Both the site staff and Pittsburgh/ETUDES trained research staff will make the family aware that they do not have to immediately make the decision to consent and can take the time to think and discuss participation after they receive all the necessary consent and risk information. The staff may also say that their participation will not influence their care or relationship with care providers. The staff will encourage the family to discuss their participation and provide several minutes for adequate reflection time.

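### BRITEPath youth are counted and given their baseline call after completed onboarding, with no calls planned for consented non-completers and no matching entry point for TAU

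*Combined protocol and SAP*

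**What the plan says.** All references are to the combined protocol and SAP.

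- **Who is counted.** Section 12.0 expects about 10 subjects at each site, described "as eligible and completed informed consent, and intervention with site clinicians". Section 26.0 gives the total: "26.1 Study-Wide Number of Subjects: 50". The split between TAU and BRITEPath is not stated.
- **When onboarding happens.** Section 22.0: "Upon obtaining informed consent, the site staff will initiate the BRITEPath intervention". Section 13.0: "Participants are provided with the BRITE app during this appointment following completion of the intervention".
- **When research calls happen.** The payment list in Section 13.0 has a "Baseline visit phone call after intervention completed at site", then week 4 and week 12 calls. Section 22.0: "Following the intervention, Pittsburgh/ETUDES Center research staff will follow up and complete research phone calls for which participants will be paid".
- **The other time anchor.** Section 2.0 plans to assess impact "by obtaining follow-up phone assessments on suicidality, depression, and functional status at 4 and 12 weeks after intake".
- **TAU.** Section 17.0 says that "all practices start with TAU (i.e., PCP referral to embedded MH care"). No section says how a TAU-period patient is enrolled, when that patient counts, or when the baseline call is made.
- **Not stated anywhere.** There is no analysis population, no intention-to-treat rule, and no instruction for a youth who consents but does not complete onboarding.

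**The concern.** In a stepped-wedge comparison, the point at which a person becomes a study subject should be the same event in both conditions and should come before anything the condition itself can influence. Completing BRITEPath onboarding is not such an event: it comes after assignment, depends on the intervention, and has no counterpart in TAU.

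Three things are at stake:

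1. **The Hypothesis 1b contrast.** If the entry point is applied as worded, outcomes in BRITEPath periods come from youth who finished onboarding, and outcomes in TAU periods from patients who had no such step.
2. **The feasibility criterion.** Section 2.0 requires 75% use with recipients of BRITEPath as the denominator. Consented youth who never received it are outside that denominator, although failure to onboard is itself a feasibility result.
3. **What comes next.** Section 6.0 intends the effect-size estimates to inform the design of a larger trial, so a selection effect here would carry forward.

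Non-completion is foreseeable. Safety planning is part of onboarding (Section 5.0), and the risk-management text in Section 6.0 provides for adolescents who cannot commit to a safety plan or are at high imminent risk. Those youth may be among the more severely ill.

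**Working it through.** **1. The plan's own figure.** Section 17.0 gives a 95% confidence interval width of at most 0.28 for n = 50. The Wald width at a proportion of 0.5 is 2 × 1.96 × √(0.5 × 0.5 / 50) = 0.277, so the figure reproduces. It concerns precision and does not test who is counted or when.

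**2. The sections side by side.** Three youths, each eligible and consented:

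| Youth | Within the Section 12.0 description? | Baseline call under Section 13.0? | Week 4 and 12 calls |
|---|---|---|---|
| BRITEPath period, onboarding completed | Yes | Yes | Planned |
| BRITEPath period, onboarding not completed | No | The event it follows has not occurred | After the intervention in Section 22.0; from intake in Section 2.0; not reconciled |
| TAU period | Cannot be applied | Cannot be applied | From intake in Section 2.0; otherwise not described |

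The second row has no explicit plan, and the third has no entry rule at all.

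**3. Size of a selection effect on the outcome mean.** Let p be the share of consented BRITEPath youth who do not complete onboarding, and d the amount, in SD, by which their outcomes are worse than those of completers. If completers have mean C, all consented youth have mean (1 − p) × C + p × (C − d) = C − p × d. The completers' mean is therefore better by p × d. The documents give neither p nor d. Assumed values:

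- p = 10%, d = 0.3: 0.10 × 0.3 = 0.03 SD
- p = 20%, d = 0.5: 0.20 × 0.5 = 0.10 SD
- p = 30%, d = 0.7: 0.30 × 0.7 = 0.21 SD

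If non-completers did better than completers, the sign would reverse.

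**4. Effect on the use criterion.** Assume that a recipient is a youth who completed onboarding. The app is provided only then, so non-completers contribute no use. If exactly 75% of recipients use it, use among all consented is 0.75 × (1 − p):

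- p = 10%: 0.75 × 0.90 = 67.5%
- p = 20%: 0.75 × 0.80 = 60%
- p = 30%: 0.75 × 0.70 = 52.5%

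**5. Consents behind a completion-based count.** As an upper illustration, suppose all 50 were counted only on completion. The consents needed are 50 / (1 − p), rounded up: 56, 63 and 72 for p = 10%, 20% and 30%. That leaves 6, 13 and 22 consented youth outside the count. Because the 50 must also hold TAU patients, the actual numbers would be smaller.

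**The case against.** The strongest reply is that order is being read as a condition. Section 13.0 is a payment list and Section 22.0 a description of workflow. Neither says that calls are withheld if onboarding is incomplete, and only the baseline line mentions completion. Section 2.0 already times the week 4 and week 12 assessments from intake. Read literally, Section 12.0 would stop any TAU patient from being counted, which suggests loose wording about the intervention stage. Much of this stands: the text does not show that non-completers would be refused follow-up. But it does not plan their follow-up either, and a site following it has nothing to act on.

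Three stronger readings are tempting, and the documents do not support them:

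- *Non-completers are replaced.* Section 12.0 is an expectation of about 10 per site. No replacement rule is written; replacement is an inference from a count worded in completers.
- *Non-completers leave no outcome data.* Section 6.0 lists PHQ-9 scores and service use from the medical record, and contact details are entered once eligibility is established. Sections 23.0 and 24.0 log the consent response with date and time, and Section 18.0 keeps a CONSORT diagram and reports early termination to the DSMB. Early stopping need not be hidden. However, the C-SSRS and quality-of-life ratings come from the calls, and record permission is given verbally by phone, so access for a youth who is never called is unclear. The Reach comparison in Section 17.0 covers characteristics, not outcomes.
- *TAU is known to be unfiltered.* TAU enrolment is not described, so the asymmetry is inferred. What can be said is that a rule based on completing BRITEPath cannot be applied in TAU.

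The loss may also be small. Onboarding is planned at 30 minutes, starts on consent and ends in the same appointment, and owning a suitable device is an inclusion criterion. With an assumed 25/25 split and no clustering, the 95% half-width for a difference is 1.96 × √(2/25) = 0.55 SD, against which 0.03 to 0.10 SD is small. That is fair for this pilot's own inference. It is a weaker answer for an estimate meant to inform a later trial, because the bias does not shrink as the sample grows.

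**Conclusion.** The point holds as a defect in the definition of study entry. Sections 12.0, 13.0 and 22.0 tie the BRITEPath count and baseline call to completed onboarding, plan no calls for consented non-completers, and are not reconciled with the intake anchor in Section 2.0. The same entry point cannot be used in TAU, for which none is given. Followed as written, the plan selects BRITEPath youth after assignment for the Hypothesis 1b contrast.

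The documents do not establish that bias will occur, or how much. The illustrative 0.03 and 0.10 SD rest wholly on assumed stop rates and outcome gaps, and 0.21 SD needs a 30% stop rate that nothing in the documents supports. The direction in favour of BRITEPath is plausible but not shown. The use criterion is the more sensitive of the two: a 10% stop rate alone would turn 75% among recipients into 67.5% among all who consented. The correction is cheap and should be made.

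**What to change.** Amend Sections 12.0, 13.0 and 22.0 as follows:

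1. Define an enrolled subject, in both conditions, as one who is eligible and has consented, whether or not onboarding is completed.
2. Time the baseline, week 4 and week 12 calls from intake or consent in both conditions, including for youth who never start or finish onboarding. State which date is used, so that these sections agree with Section 2.0.
3. Analyse each participant under the clinic's condition on the consent date.
4. Report by clinic the number who consented but were not onboarded, and show use both among recipients and among all who consented. A completers-only estimate of the effect can be given as secondary.

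This removes the dependence on completion. Because onboarding starts on consent, many baseline calls may still fall after it, and the amended text should say so.

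The cost is protocol wording, a changed call trigger in the study database, and a few calls within the 50 to youth who did not use the app. The effect and use estimates may come out slightly less favourable. Clinical care is unchanged.
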